## 4 List of Analyses

### 4.1 Recruitment and retention

Number of patients assessed for eligibility; number of patients who were excluded (with a tabulation of reasons for exclusion); number of patients who were randomised; number of randomised patients who withdrew consent including to use of data; number of patients allocated to each treatment arm; number of patients who completed full follow-up to 90 days or died in that period; number from first randomised who completed follow-up to 180 days for EQ-5D; with a tabulation of reasons for discontinuing early, number of patients included in ITT analysis of main clinical outcome, by allocated treatment and overall; number of patients in safety analysis population, by treatment received and overall.

Graph of cumulative number randomised over time.

Dates first and last patients randomised.

A tabulation of numbers of patients randomised by study site, split by allocated treatment (and overall). For EudraCT reporting purposes, enrolment will also be summarised into age

categories 18-64; 65-84; and 85+ years.

## 4.2 Baseline data

A table showing baseline demographic and clinical characteristics overall and by allocated intervention will include:

- a) Age (at randomisation in years)
- b) Sex (Male / Female)
- c) NEWS Score including individual components (1. Respiratory rate, 2. Oxygen saturations, 3. Temperature, 4. Systolic blood pressure, 5. Heart rate, 6. Glasgow Coma Scale (GCS))
- d) Lactate (mmol/l)
- e) Vital signs (pulse (bpm), systolic and diastolic blood pressure (mmHg), fraction of inspired oxygen (FiO2) (%))
- f) Routine blood results (glucose (mmol/L), eGFR (mL/min/1.73m^2), albumin (g/l), ALT (U/L or iU/L), troponin (ng/l), urea (mmol/L), creatinine (μmol/L), WCC (x10^9/L), Hb (g/l), platelets (x10^9/L), neutrophils (x10^9/L), CRP (mg/l), procalcitonin (ug/L or ng/mL)).
- g) Expected source of infection (chest, urine, CNS, skin, abdomen, missing, unknown, other)
- h) Co-morbidities (cancer, stroke, MI, peripheral vascular disease, heart failure, cardiac obstructive pulmonary disease, chronic kidney disease, diabetes type I/ II & dementia)
- i) Average volume of fluid (mL) given prior to randomisation.

No formal statistical testing of the baseline characteristics will be performed. The first relevant observation will be presented if more than one observation was collected.

## 4.3 Trial treatment details, and adherence

No formal statistical testing will be performed.

The protocol defines:

**Crossover** Any participant who receives the intervention from the arm they were not allocated to within 24 hours of randomisation will be defined as a crossover and does not need to be recorded as a deviation.

**Non-adherence** This will be defined as to have occurred in any participant who has not received their allocated fluid prescription for resuscitation within 6 hours of the randomisation and does not need to be recorded as a deviation.

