### **6.3 DOSING REGIME**

Participants allocated to the treatment arm will receive intravenous 5% Human Albumin Solution (HAS) administered as the sole intravenous resuscitation fluid during the initial 6-hour resuscitation period. It is anticipated that most participants will receive approximately 10ml/kg in the first 3 hours using 250-500ml rapid infusion (bolus) of HAS for resuscitation based on clinical judgement, using clinical assessment supplemented by technology within the usual scope of practice. After 3 hours, further HAS boluses for resuscitation up to 6 hours post-randomisation will be at clinical discretion and will be documented in the eCRF. Both vital signs and lactate, if measured, prior to treatment starting and at 1,3,5,7 hours (+/-30mins) after randomisation, will be recorded in the eCRF as well as source data worksheets or medical notes.

To avoid contamination, participants in the HAS arm should not receive balanced crystalloid or other fluid as a resuscitation fluid in the first 6 hours post randomisation. If the treating clinician believes resuscitation to euvolaemia has been completed within the 6hour period post randomisation and wishes to commence slow maintenance fluid within this timeframe using balanced crystalloid, this should be at a rate of no more than 125ml/hour. The reason for the fluid should be clearly recorded in the eCRF i.e., maintenance rather than resuscitation. In the subsequent event of further clinical deterioration during the intervention timeframe requiring resuscitation fluid, further boluses of HAS should be administered and documented as further bolus fluid for resuscitation.

Participants allocated to the usual care arm will receive intravenous balanced crystalloid administered as the sole intravenous fluid during the initial 6 hour resuscitation period post randomisation. It is anticipated that most participants will receive approximately 30ml/kg in the first 3 hours using 250-1000ml rapid infusion (bolus) of balanced crystalloid for fluid resuscitation based on clinical judgement, using clinical assessment supplemented by technology within the usual scope of practice. Thereafter, further crystalloid boluses for resuscitation up to 6 hours will be at the discretion of the clinical team and will be documented in the eCRF. Both vital signs and lactate, if measured, prior to treatment starting and at 1,3,5,7 hours (+/-30mins), will be recorded in the eCRF as well as source data or medical notes.

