## **6.5 CROSSOVER OF TREATMENT ARMS**

If a participant receives the intervention from the arm they were not allocated to within 24 hours of randomisation then this will be recorded as an outcome in the eCRF at discharge. This does not need to be reported to the Sponsor as a deviation/violation.

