### Trial treatment details

Table: Per treatment group, who received their allocated fluid for resuscitation within hours, a table showing the following:

- a) Yes, within 75% of that allocated and did not cross over within 0 to 6 hours
- b) Yes, within 75% of that allocated and did cross over within 0 to 6 hours
- c) Yes, at least 200mls administered, regardless of whether crossover occurred
- d) Some received but between 6 hours and less than 12 hours, regardless of whether crossover occurred
- e) Some received but between 12 and less than 24 hours, regardless of whether crossover occurred
- f) None received or unknown.

Graph: The cumulative distribution function for each of volume and % of allocated

resuscitation fluid received, by treatment group, will be plotted separately for each of the time windows 0-6 hours; 0-12 hours; 0-24 hours; 6-24 hours.

Graph: Kaplan-Meier curves will be plotted, by treatment group, for time to crossover.

Further, adherence per treatment group will summarised descriptively using the following measures:

- 1) Time to start of IMP (randomisation to treatment)
- 2) Proportion of patients who received their allocated intervention for fluid resuscitation
- 3) Proportion of patients who received their allocated intervention for maintenance
- 4) Proportion of patients who received crossover fluid in to 6 hours and volume of crossover fluid received
- 5) Proportion of patients who received crossover fluid in to 24 hours and volume of crossover fluid received
- 6) Completion rates for initial bolus administration (within first 6 hours)
- 7) Proportion of patients who receive any other fluid apart from intervention or control during first 6 hours.

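### SAP 4.3 does not limit crossover by purpose: read literally, it counts the balanced-crystalloid maintenance that Protocol 6.3 permits as crossover, in the HAS arm only

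*SAP*

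**What the plan says.** **Crossover.** SAP 4.3 states: "Any participant who receives the intervention from the arm they were not allocated to within 24 hours of randomisation will be defined as a crossover". It presents this as the protocol's definition, and Protocol 6.5 has the same rule: "If a participant receives the intervention from the arm they were not allocated to within 24 hours of randomisation then this will be recorded". Sites enter this outcome on the eCRF when the patient is discharged. Neither text sets a limit by purpose, rate or minimum volume.

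**Non-adherence.** The next definition in SAP 4.3 does carry such a limit. It covers "any participant who has not received their allocated fluid prescription for resuscitation within 6 hours of the randomisation".

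**Permitted maintenance.** Protocol 6.3 bars balanced crystalloid in the HAS arm only as a resuscitation fluid, and only for the first 6 h. If the clinician considers resuscitation complete and "wishes to commence slow maintenance fluid within this timeframe using balanced crystalloid, this should be at a rate of no more than 125ml/hour". It adds: "The reason for the fluid should be clearly recorded in the eCRF i.e., maintenance rather than resuscitation". For controls, 6.3 makes balanced crystalloid the sole intravenous fluid of the 6 h period and allows maintenance under the same rate cap.

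**Outputs by arm that use crossover within 6 h.** These are rows (a) and (b) of the treatment table, which differ only in whether crossover occurred in 0 to 6 h; the Kaplan-Meier curves for time to crossover; and measure 4, "Proportion of patients who received crossover fluid in to 6 hours and volume of crossover fluid received".

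**The concern.** The regimen and the reporting rule do not fit together. Protocol 6.3 treats slow balanced crystalloid after HAS resuscitation as correct care. The crossover rule, taken at its word, treats the same infusion as receipt of the other arm's intervention. Because the permitted maintenance fluid is the control arm's own product, the mismatch can arise only among HAS patients.

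Protocol 6.4 makes adherence a feasibility outcome, and the trial exists to inform a definitive study. A table with clearly more crossover under HAS than under crystalloid could be taken to mean that HAS is hard to deliver as sole resuscitation fluid, when part of the difference is care that the protocol allows. The wording also leaves room for two programmers to build different tables from the same fluid records.

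**Working it through.** **1. Two patients treated exactly as Protocol 6.3 allows.** Each receives only the allocated fluid for resuscitation, enough to meet the 75% condition of rows (a) and (b). Each then starts balanced-crystalloid maintenance at hour 4, within the rate cap.

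| Output in SAP 4.3 | HAS patient | Control patient |
|---|---|---|
| Crossover definition, taken literally | Yes | No |
| Measure 4 (crossover to 6 h) | Counted, with volume | Not counted |
| Treatment table | Row (b) | Row (a) |
| Time-to-crossover curve | Event at hour 4 | No event |
| Non-adherence | No | No |
| Measure 2, "Proportion of patients who received their allocated intervention for fluid resuscitation" | Yes | Yes |

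The first four lines differ although both patients were managed as intended. The last two agree because those items are tied to resuscitation.

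**2. Does the word intervention already imply resuscitation?** Within the SAP it does not. Measure 2 applies the word to resuscitation, and measure 3 applies it to maintenance: "Proportion of patients who received their allocated intervention for maintenance". In this section it therefore names a product, and the purpose is added when it is meant. Measure 4 adds none.

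**3. Counts.** The plan gives no figure to reproduce here.

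- Arm size: 300 randomised 1:1 (Protocol 4.1 and 5.5.1), so 300 / 2 = 150 HAS patients.
- x = share of HAS patients who truly cross over for resuscitation (assumed).
- m = share of the remaining HAS patients who receive permitted balanced-crystalloid maintenance (assumed; the documents give no value).
- Reported HAS crossover = x + (1 - x)m. Added by maintenance = 150(1 - x)m patients.

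| m | Added, x = 0 | Added, x = 5% | Added, x = 10% | Reported HAS crossover, x = 5% |
|---|---|---|---|---|
| 10% | 15 | 14.25 | 13.5 | 14.5% |
| 30% | 45 | 42.75 | 40.5 | 33.5% |
| 50% | 75 | 71.25 | 67.5 | 52.5% |
| 70% | 105 | 99.75 | 94.5 | 71.5% |

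With the same x in both arms, the control arm reports x: 5% where the HAS arm reports 14.5% to 71.5%. If crossover is limited to resuscitation use, both arms report 5%.

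**4. Volume in measure 4.** At the cap, maintenance from hour 5 adds 125 x 1 = 125 mL by hour 6, and from hour 3 it adds 125 x 3 = 375 mL. The arithmetic ceiling is 125 x 6 = 750 mL, which would leave no time for resuscitation first. The start times are assumptions.

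**5. After 6 h.** The definition runs to 24 h, whereas the restriction in 6.3 ends at 6 h. Balanced crystalloid given to a HAS patient between 6 and 24 h is therefore also crossover on the literal wording, although no protocol rule advises against it.

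**The case against.** The strongest reply is that the rule should be read in context. Protocol 5.5.2 describes each arm by its sole resuscitation fluid, 6.3.1 says the arms differ only in resuscitation fluid, 6.3 frames contamination as other fluid given for resuscitation, and the title line of the treatment table in SAP 4.3 refers to resuscitation. Crossover is also an item that sites enter at discharge, and staff working under 6.3 may well not record permitted maintenance. This reading is reasonable and may be what was intended. But it is not written into the definition, the SAP's use of the allocated intervention for maintenance points the other way, and no document says whether the tables will come from the site's entry or from fluid volumes. Even on this reading, no line in SAP 4.3 directly reports balanced-crystalloid maintenance in HAS patients, because measure 7 excludes both trial fluids.

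It is also fair to say that the stakes are limited. SAP 4.3 plans no formal testing, and the documents state no progression threshold that uses crossover. Showing all other-arm fluid is informative about separation between arms. That argues for reporting maintenance under its own label, not for leaving it out.

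Some stronger inferences are tempting and are not supported:

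- **That the mortality comparison is biased.** The main model follows allocation and does not use crossover. The compliance analysis in SAP 4.6(a) is framed on cumulative dose, and no stated link to the crossover definition exists.
- **That measure 5 merges 0-6 h with later fluid.** Its lower time bound is not legible in the text available, so nothing can be said about pooling or about how much of its volume falls after 6 h.
- **That measure 3 has the same fault.** It does not use the crossover definition. It describes which fluid was used for maintenance.

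**Conclusion.** The point holds as a defect of definition with a one-sided effect. As written, the rule classes HAS patients who receive maintenance permitted by Protocol 6.3 as crossovers in measure 4, rows (a)/(b) and the Kaplan-Meier curve, and does not do so for controls given the same fluid. Each 10% of 150 HAS patients adds up to 15 crossovers (10 percentage points); with 5% already crossed over, about 14 (9.5 points). The actual size is unknown because the documents give no maintenance share, so the larger entries in the table above are illustrations, not forecasts.

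The conclusion rests on the literal reading, which the SAP's own vocabulary favours but does not compel. It concerns descriptive adherence outputs only. The primary estimates, the non-adherence definition and measure 2 are unaffected. It is worth correcting because adherence is a named feasibility outcome and the remedy is small.

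**What to change.** Change SAP 4.3, with a note that it refines Protocol 6.5 for reporting:

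1. For 0-6 h, count as crossover only the other arm's fluid recorded in the eCRF as given for resuscitation. Use this for measure 4, rows (a)/(b) and the 0-6 h part of the Kaplan-Meier curve. State that it is derived from the fluid records.
2. Report the other arm's fluid given as maintenance in 0-6 h on a separate line, by arm, with volume.
3. Keep the 24 h window of Protocol 6.5, but report receipt of the other arm's fluid in 6-24 h separately from 0-6 h, split by purpose where recorded. Later resuscitation with the other arm's fluid, such as HAS given to a control at hour 8, then still counts. SAP 4.6 already divides randomised fluid volume at 6 h.

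The cost is one reworded definition, one added line and one split by time. No new data are needed for 0-6 h: Protocol 6.3 requires the reason for maintenance fluid in both arms, and 8.1 collects timing and volume. No protocol amendment is proposed, since the SAP abstract reports that 300 participants were recruited. The downside is that purpose in 0-6 h relies on a reason recorded by an unblinded clinician, who could label resuscitation as maintenance. Showing the maintenance line with its volume lets a reader judge that.

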### Trial treatment details

Table: Per treatment group, who received their allocated fluid for resuscitation within hours, a table showing the following:

- a) Yes, within 75% of that allocated and did not cross over within 0 to 6 hours
- b) Yes, within 75% of that allocated and did cross over within 0 to 6 hours
- c) Yes, at least 200mls administered, regardless of whether crossover occurred
- d) Some received but between 6 hours and less than 12 hours, regardless of whether crossover occurred
- e) Some received but between 12 and less than 24 hours, regardless of whether crossover occurred
- f) None received or unknown.

Graph: The cumulative distribution function for each of volume and % of allocated

resuscitation fluid received, by treatment group, will be plotted separately for each of the time windows 0-6 hours; 0-12 hours; 0-24 hours; 6-24 hours.

Graph: Kaplan-Meier curves will be plotted, by treatment group, for time to crossover.

Further, adherence per treatment group will summarised descriptively using the following measures:

- 1) Time to start of IMP (randomisation to treatment)
- 2) Proportion of patients who received their allocated intervention for fluid resuscitation
- 3) Proportion of patients who received their allocated intervention for maintenance
- 4) Proportion of patients who received crossover fluid in to 6 hours and volume of crossover fluid received
- 5) Proportion of patients who received crossover fluid in to 24 hours and volume of crossover fluid received
- 6) Completion rates for initial bolus administration (within first 6 hours)
- 7) Proportion of patients who receive any other fluid apart from intervention or control during first 6 hours.

#### **4.4 Primary outcome**

1) This will be the proportion of those screened who were randomised (number randomised/ number screened) with a 95% CI.

2) The main clinical outcome is 30-day mortality, under intravenous 5% Human Albumin compared with intravenous balanced crystalloid in the early resuscitation phase of management of adults with community acquired sepsis.

A mixed effects logistic regression model will be used, including a fixed effect for intervention group adjusted for site (as a random effect) and baseline covariates known to be strong predictors of 30-day mortality (age; active cancer; heart failure). The intervention effect will be reported as an odds ratio and 95% confidence interval. The assumptions for mixed effects logistic regression will be assessed to ensure compliance. If this model proves inappropriate, a suitable alternative will be used.

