### **2.2 ENDPOINTS**

#### **2.2.1 Primary Endpoint**

1. Recruitment rate from screening logs
2. 30-day mortality

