### **5.3 SCREENING FOR ELIGIBILITY**

Participant eligibility will be verified by a clinical trial physician. Confirmation of eligibility will be recorded on the eligibility form/eCRF and within the participants' medical records.

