## 10. STATISTICS AND DATA ANALYSIS

### 10.1 SAMPLE SIZE CALCULATION

A pragmatic sample size of 300 was based on projected recruitment over 12 months study period in around 15 centres. It is anticipated that this will provide sufficient data to demonstrate feasibility and inform design of a fully powered study

As a pilot feasibility study, no formal sample size calculation is appropriate. However, indicatively on the first primary outcome of recruitment feasibility, an acceptance rate of 50% would be estimated with a 95% confidence interval of 44% to 56% if 300 from 600 of those eligible agreed to be randomised. For the second primary outcome of death at 30 days, indicatively if the standard of care had a 30-day mortality of 35%,

with 300 randomised the study would have 90% power at a 5% level of significance to detect an approximate 50% relative reduction of 17%, to 18%.

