## 10.2 PROPOSED ANALYSES

All statistical analyses will be governed by a comprehensive Statistical Analysis Plan authored by the study statistician and agreed by the independent Trial Steering Committee. As a feasibility pilot trial, all analyses will be exploratory and mainly descriptive. The primary outcome of recruitment feasibility will be assessed as the proportions who visited the ED that were (a) eligible, and then (b) of those who were eligible that were approached and then (c) of those eligible and approached the proportion that consented to be randomised. The clinical primary outcome of all causes mortality at 30 days will be summarised by randomised treatment group and then analysed using a mixed effects logistic regression adjusting for site and adjusting for pre-specified baseline covariates known to be strong predictors of 30-day mortality. The range of possible treatment effects indicated by the 95% confidence interval around the estimate of difference in 30-day mortality, and that around the 30-day mortality rate in the standard of care group will be used to inform the design of a definitive trial. We plan a number of important predefined exploratory sub-group analyses on the primary outcome including severity of illness at recruitment (NEWS/NEWS2, qSOFA, lactate), age, pre-existing known heart failure, pre-existent chronic kidney disease, baseline albumin. We will also undertake a subgroup analysis of primary outcome for all patients not admitted to a critical bed (HDU or ICU) If the data permits, we will consider additional analyses exploring compliance (what cumulative dose of novel intervention or standard care was received) using causal models with an instrumental variable approach. Secondary outcomes (e.g. volume of intravenous fluid, length of stay) will be analysed using mixed effects linear models, while the secondary outcomes involving proportions (e.g. proportion receiving renal replacement therapy, vasopressor infusion, invasive ventilation, readmissions within 90 days) will be analysed as per the primary outcome (with a mixed effects logistic regression). The proportions admitted to critical care (HDU or ICU) will be analysed using a proportional odds logistic regression. The safety outcomes will be analysed in a similar way according to their distribution. The quality of life data (at 180 days) will be analysed likewise with a model appropriate to the distribution. We will be interested in understanding the observed patterns of any missing data.

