## 2 Statistical Methods section from the protocol

*All statistical analyses will be governed by a comprehensive Statistical Analysis Plan authored by the study statistician and agreed by the independent Trial Steering Committee. As a feasibility pilot trial, all analyses will be exploratory and mainly descriptive. The primary outcome of recruitment feasibility will be assessed as the proportions who visited the ED that were (a) eligible, and then (b) of those who were eligible that were approached and then (c) of those eligible and approached the proportion that consented to be randomised. The clinical primary outcome of all causes mortality at 30 days will be summarised by randomised treatment group and then analysed using a mixed effects logistic regression adjusting for site and adjusting for pre-specified baseline covariates known to be strong predictors of 30-day mortality. The range of possible treatment effects indicated by the 95% confidence interval around the estimate of difference in 30-day mortality, and that around the 30-day mortality rate in the standard of care group will be used to inform the design of a definitive trial. We plan a number of important predefined exploratory sub-group analyses on the primary outcome including severity of illness at recruitment (NEWS/NEWS2, qSOFA, lactate), age, pre-existing known heart failure, pre-existent chronic kidney disease, baseline albumin. We will also undertake a subgroup analysis of primary outcome for all patients not admitted to a critical bed (HDU or ICU) If the data permits, we will consider additional analyses exploring compliance (what cumulative dose of novel intervention or standard care was received) using causal models with an instrumental variable approach. Secondary outcomes (e.g. volume of intravenous fluid, length of stay) will be analysed using mixed effects linear models, while the secondary outcomes involving proportions (e.g. proportion receiving renal replacement therapy, vasopressor infusion, invasive ventilation, readmissions within 90 days) will be analysed as per the primary outcome (with a mixed effects logistic regression). The proportions admitted to critical care (HDU or ICU) will be analysed using a proportional odds logistic regression. The safety outcomes will be analysed in a similar way according to their distribution. The quality of life data (at 180 days) will be analysed likewise with a model appropriate to the distribution. We will be interested in understanding the observed patterns of any missing data.*

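### Protocol 10.1's 95% interval for 300 of 600 should be 46% to 54%, not 44% to 56%; and SAP 4.4(1) reduces the three-step recruitment analysis of Protocol 10.2 to one ratio with an undefined denominator

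*SAP*

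**What the plan says.** Recruitment feasibility is the first of two primary outcomes. Protocol 2.2.1 labels the endpoint "Recruitment rate from screening logs" and gives no denominator.

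Protocol 10.2 says how it will be assessed, in three sequential proportions. The first is "the proportions who visited the ED that were (a) eligible". The second, in the text that SAP section 2 repeats, is the share "of those who were eligible that were approached". The third is "c) of those eligible and approached the proportion that consented to be randomised".

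The SAP's own analysis, in section 4.4 item 1, is a single ratio: "This will be the proportion of those screened who were randomised (number randomised/ number screened) with a 95% CI". *Screened* is not defined there. The flow counts in SAP 4.1 begin "Number of patients assessed for eligibility; number of patients who were excluded (with a tabulation of reasons for exclusion" and go on to the number randomised. They do not list the numbers eligible, approached or declined. Protocol 5.3 is headed "SCREENING FOR ELIGIBILITY", and Protocol 5.4 requires eligible patients who were not recruited to be entered on the screening log.

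Protocol 10.1 illustrates the precision of a 50% acceptance rate as a "95% confidence interval of 44% to 56% if 300 from 600 of those eligible agreed to be randomised".

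**The concern.** There are two separate matters.

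First, the interval in Protocol 10.1 looks too wide for 600 observations. It is the only precision the protocol states for this primary outcome.

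Second, the protocol breaks recruitment into steps and the SAP's analysis sections do not. SAP section 2 quotes the three proportions, but quoting them does not schedule them as analyses, and no reason is given for using a different measure. The study exists to inform a larger definitive trial. Few eligible patients, eligible patients missed by the research team, and refusal each call for a different change to that trial, and one overall ratio cannot say which occurred. The ratio also depends on whom each site's log captured, so its denominator needs a definition.

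**Working it through.** **1. The interval in Protocol 10.1**

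Inputs: x = 300, n = 600 (Protocol 10.1); two-sided 95% (SAP section 3).

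Wald half-width = 1.96 × √(p(1 − p)/n) = 1.96 × √(0.25/600) = 0.040, so 46.0% to 54.0%. Other methods for 300/600:

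| Method | 95% CI |
|---|---|
| Wilson, Agresti-Coull, Jeffreys | 46.0% to 54.0% |
| Clopper-Pearson exact | 45.9% to 54.1% |
| Wald with continuity correction | 45.9% to 54.1% |

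All round to 46% to 54%. The stated 44% to 56% is not reproduced.

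What would reproduce it:
- A half-width of 6 points at 95% needs n = 0.25 × (1.96/0.06)² ≈ 267, or 227 to 317 if the half-width was rounded from anywhere between 6.5 and 5.5 points.
- With n = 300: 1.96 × √(0.25/300) = 0.057, so 44.3% to 55.7%, which rounds to the stated figures.
- With n = 600, a 6-point half-width would be about a 99.7% interval, or would need a design effect of about 1.9 to 2.2. Neither is mentioned.

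**2. Which planned output supplies which step**

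| Protocol 10.2 step | Calculated in SAP section 4? | Obtainable from required records? |
|---|---|---|
| (a) eligible / ED visits | No | Numerator yes: randomised plus logged eligible non-recruited (Protocol 5.4). Denominator no: the assessments and data items in Protocol 7.1 and 8.1 include no count of ED visits |
| (b) approached / eligible | No | Number approached not listed |
| (c) consented / (eligible and approached) | No | Only if exclusion reasons separate not approached from declined, which the SAP does not say |

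The illustration in Protocol 10.1 uses yet another denominator, randomised/eligible, which is (b) × (c) if those who consent are those randomised.

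**3. What one ratio hides**

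Illustrative counts; those screened stand in for ED visits, and consented and randomised are taken as the same 300.

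| Screened | Eligible | Approached | Randomised | (a) | (b) | (c) | Randomised/screened |
|---|---|---|---|---|---|---|---|
| 3,000 | 600 | 600 | 300 | 20% | 100% | 50% | 10% |
| 3,000 | 1,500 | 300 | 300 | 50% | 20% | 100% | 10% |
| 3,000 | 1,500 | 1,500 | 300 | 50% | 100% | 20% | 10% |

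Each row multiplies to 0.10. Deriving the number eligible from Protocol 5.4 separates the first row from the other two. It cannot separate the second from the third: both have 1,500 eligible and 1,500 − 300 = 1,200 eligible but not recruited. For that, the number approached is needed.

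**4. How far the ratio depends on the denominator**

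Take 300 randomised of 600 eligible, as in Protocol 10.1. The documents give no share of screened patients who are eligible, so 80% and 20% are assumptions.

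| Meaning of screened | Screened | Ratio (Wald 95% CI) |
|---|---|---|
| Eligible only | 600 | 50% (46.0% to 54.0%) |
| All assessed, 80% eligible | 600/0.8 = 750 | 40% (36.5% to 43.5%) |
| All assessed, 20% eligible | 600/0.2 = 3,000 | 10% (8.9% to 11.1%) |

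**The case against.** The best defence is that randomised/screened is a fair form of the endpoint as Protocol 2.2.1 labels it, and that Protocol 10.2 itself hands the analyses to the SAP. That stands. A reader might infer that the SAP analyses the wrong endpoint; the label does not support that. What is missing is the breakdown promised in Protocol 10.2.

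A reader might also infer that none of the steps can be recovered. That goes too far. SAP 4.1 tabulates reasons for exclusion, and the logging in Protocol 5.4 together with those randomised gives the number eligible. Only the split between not approached and declined is left unassured.

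Nor is *screened* wide open. Protocol 5.3 and SAP 4.1 both point to everyone assessed for eligibility. The spread from 50% to 10% combines a less natural reading with assumed shares, so it shows sensitivity and does not estimate the size of the problem in this trial.

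It is tempting to ask for proportion (a) exactly as Protocol 10.2 words it. The documents do not support that either: no listed data item counts ED visits, and Protocol 3 and 4.1 also recruit from Medical and Surgical Assessment Units.

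Finally, all analyses are exploratory and mainly descriptive, and no progression threshold is tied to the ratio. That limits the weight of the point but does not remove the need for stated denominators.

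**Conclusion.** Both parts hold, at moderate weight.

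The interval for 300 of 600 is 46% to 54% by every standard 95% method. The stated 44% to 56% fits a denominator of 300. That 300 was actually used is an inference, since the documents do not say so. A reader might take the error as a flaw in the sample size. It is not: Protocol 10.1 calls the illustration indicative and bases the 300 on projected recruitment. The error makes the half-width about 6 points instead of 4, so precision looks worse than it is.

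SAP 4.4(1) replaces three protocol-specified proportions for a primary outcome with one ratio, without explanation. That ratio cannot separate eligibility, missed approach and refusal. The number eligible is recoverable if sites logged as Protocol 5.4 requires; the numbers approached and declined may not be. The loss is in what the feasibility result can tell the designers of the definitive trial, and no decision rule in the documents is affected.

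**What to change.** - **SAP 4.4(1):** define *screened*, naturally as all patients assessed for eligibility, as in SAP 4.1. Keep randomised/screened. Beside it report eligible/screened, approached/eligible and consented/(eligible and approached), each with a 95% CI, and mark any that the logs cannot support as not available.
- **Same section:** state that screened replaces ED visits as the denominator of (a), that this departs from Protocol 10.2, and why: ED visits are not among the listed data items, and recruitment also takes place in assessment units.
- **SAP 4.1:** add the numbers eligible and approached.
- **Protocol 10.1:** restate the interval for 300 of 600 as 46% to 54%.

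The cost is SAP wording, a few table rows and one corrected interval. The SAP abstract describes recruitment in the past tense, so log content may already be fixed and some steps may have to be reported as not available.
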